10.2. Populations for Analyses

The primary population of interest is the pharmacodynamic per-protocol (PDPP) population as defined in Table 3.

Table 3 Description of Analysis Populations

Population	Description
Screened Population	All participants who signed an ICF to participate in the clinical trial. This population will be used for summarizing screening failure rates and reasons for screening failure.
Safety Population	All randomized participants who receive at least one dose of study treatment will be included in the safety population. This population will be used in the evaluation of safety and tolerability.
Pharmacodynamic Per-Protocol (PDPP) Population	All randomized participants who provide pharmacodynamic (PD) data at Day 1 and Day 42 that meets the QC criteria (See Section 9.6.1.3) and completes the protocol without important deviations will be included in the PDPP population. This population will be used in the evaluation of all endpoints with the exception of safety endpoints.

Because the current study is designed to assess the effects of study treatment on pharmacodynamic parameters, an intent-to-treat population will not be defined.

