9.6.1.3. FBF Quality Control Criteria

After both the Day 1 and Day 42 FBF procedures, the results will be checked for data quality as defined in the Study Reference Manual (SRM). If the FBF fails the quality control (QC) criteria following the Day 42 procedure, one additional attempt may be made in a subsequent visit up to 1 week later, if the participant agrees. For participants that will have repeat FBF procedures performed, details can be found in Section 9.6.1.4.

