9.6.1.4. Delayed or Repeat FBF Procedures

Delayed FBF Procedures: In the instance that the FBF procedure needs to be delayed, participants should either continue receiving the daprodustat dispensed on Day 28, while the participants randomized to darbepoetin alfa should receive an appropriate dose on Day 42. The assessments that are scheduled to be conducted on Day 42 are to be followed (See Section 2).

Repeat FBF Procedures: If the FBF procedure is determined to be repeated for either Day 1 or Day 42, the assessments should be performed as per the SoA Table at the additional FBF visit. The PWV procedures should also be repeated.

In the instance that the Day 1 FBF procedure needs to be repeated, the participant should not be dosed with study drug until after the repeat/completed procedure. The timing of all subsequent visits will begin from that completed procedure day.

In the instance that the Day 42 FBF procedure needs to be repeated, participants should either continue receiving the daprodustat dispensed on Day 28, while the participants randomized to darbepoetin alfa should receive an appropriate dose on Day 42. The safety follow up visit will take place 7-14 days after the final procedure.

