8.1.4. Strategy for Intercurrent (Post-Randomization) Events

Due to the design of the PDPP population, only subjects who have FBF measurements for both Day 1 and Day 42 are included, and it is not possible to have missing FBF data. Therefore, no FBF data will be imputed.

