8.2.2. Summary Measure

Principle secondary endpoint: Change in the absolute FBF from Day 1 to Day 42 in response to acetylcholine

Secondary endpoints: Change in FBF ratio from Day 1 to Day 42 in response to sodium nitroprusside and L-NMMA.

Change in absolute FBF from Day 1 to Day 42 in response to sodium nitroprusside and L-NMMA.

Change in Augmentation Index (AIX, an indicator of arterial stiffness) as estimated by radial arterial pulse contours from Day 1 to Day 42.

Change in pulse wave velocity (PWV) from Day 1 to Day 42.

For the PWV dataset, there are two recorded values for each variable per day, with the option to collect a third value if the first two values varied (Refer: SRM) too much from each other. The average of the two closest absolute values will be used for analysis purposes.

If for any of these measures mentioned above, the respective procedures are repeated for Day 1 and/or Day 42, the data from the repeat visit will take place of the original Day 1 and Day 42 data respectively. Like the FBF data, a QC check will be performed for the PWV data before the final analyses. The QC check will be to assess negative and extreme values for PWV ([PWV](#)).

Descriptive statistics (n, mean, standard deviation (SD), minimum, median, maximum) will be calculated by treatment group.

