8.2.3. Population of Interest

The secondary pharmacodynamics analyses will be based on the PDPP population, unless otherwise specified.

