¹⁰ The initial dose of study treatment will be **after** the Day 1/Repeat Day 1 FBF & PWV procedures. Participants will receive **EITHER** daprodustat **OR** darbepoetin alfa.

The final dose of daprodustat will be Day 41 (i.e., the day prior to the FBF & PWV procedures), while the final dose of darbepoetin alfa will be Day 28. If repeat procedures are needed the dosing will be extended (See Section 9.6.1.4).

CONFIDENTIAL

205767

¹¹ See Section 7.2 for details on study treatment adjustment

¹² Applies only to participants on anti-coagulant therapy; further details concerning measurement of the international normalised ratio (INR) and subsequent actions can be found in the study reference manual (SRM).

¹³ If test otherwise performed within 3 months prior to first dose of study treatment, testing at screening is not required

¹⁴ The FBF & PWV assessments are to be performed following confirmation of INR < 3.0 for participants on anticoagulant therapy. The Day 42 FBF & PWV assessments can be delayed up to 1 week (i.e., Day 49), while randomization (Day 1) should be delayed until the participant's INR < 3.0 (Section 9.6.1.1).

¹⁵ Only serious adverse events (SAEs) assessed as related to study participation are collected at this visit. See [Appendix 4](#) for additional details.

¹⁶ As described in Section 9.8

¹⁷ Indicates the procedures to be performed on the repeat visits only if the visit is deemed necessary. See Section 9.6.1.4.

¹⁸ Darbepoetin is only to be given on Day 42 if a Repeat Day 42 is needed.

CONFIDENTIAL

205767

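### Augmentation index and pulse wave velocity are analysed only in participants with QC-passing forearm blood flow, and a valid Day 42 reading is replaced when an FBF failure triggers a repeat visit

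*Protocol*

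**What the plan says.** **Population.** Protocol 10.2 (Table 3) defines the PDPP as "All randomized participants who provide pharmacodynamic (PD) data at Day 1 and Day 42 that meets the QC criteria (See Section 9.6.1.3"), provided the participant also completes without important deviations. It adds that "This population will be used in the evaluation of all endpoints with the exception of safety endpoints". Section 9.6.1.3 concerns FBF only: "After both the Day 1 and Day 42 FBF procedures, the results will be checked for data quality". The SAP reads the definition the same way. Section 8.1.4 states that "only subjects who have FBF measurements for both Day 1 and Day 42 are included", and 8.2.3 that "The secondary pharmacodynamics analyses will be based on the PDPP population, unless otherwise specified". Nothing is specified otherwise: Tables 3.8 to 3.10 and Listings 19 and 20, which carry AIx and PWV, are all assigned to the PDPP.

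**Repeat visits.** Protocol 9.6.1.2 and 9.6.1.3 allow one further Day 42 attempt, up to a week later, if the acetylcholine series is incomplete or FBF fails QC. Protocol 9.6.1.4 then says: "The PWV procedures should also be repeated". Under SAP 8.2.2, when a measure's own procedure has been repeated, "the data from the repeat visit will take place of the original Day 1 and Day 42 data respectively". On dosing, footnote 18 of the schedule of activities (reproduced in SAP 10.2.1) says: "Darbepoetin is only to be given on Day 42 if a Repeat Day 42 is needed".

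**The concern.** AIx and PWV are read at the radial, carotid and femoral arteries without cannulation (protocol 9.6.2). FBF needs a needle in the brachial artery and a full series of infusions (9.6.1). A failure of the second says nothing about the quality of the first. The SAP already treats them separately: 8.2.2 gives PWV its own check for negative and extreme values, 10.8.4 lists ranges for PWV and AIx, and 8.2.4 expects few missing values. None of this decides who is analysed; FBF does.

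Two things are at stake. Valid data on two secondary endpoints are left out of every planned pharmacodynamic display. And for repeat-visit participants, a sound reading at the planned timepoint gives way to a later one taken at a different interval from the last darbepoetin injection, because a different measurement failed.

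**Working it through.** The point is mainly structural, so the first steps trace the rules. The arithmetic follows.

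**1. Who is dropped.** The relevant participants have valid AIx/PWV on Day 1 and Day 42 but no QC-passing FBF pair.
- A Day 1 FBF failure leads to consideration of withdrawal before dosing (protocol 8.2), so there would normally be no Day 42 AIx/PWV to lose.
- A Day 42 failure is different. The participant has completed treatment and has both readings, but is outside the PDPP if FBF is still incomplete or failing after any repeat.
- The restriction therefore bites mainly at Day 42. SAP 10.7.1 promises that data from withdrawn participants will be listed, but a participant who completes with a failed FBF is not a withdrawal, and Listings 19 and 20 are assigned to the PDPP.

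**2. What is replaced.** The chain is: FBF incomplete or failing at Day 42, then a repeat visit, then PWV repeated, then the repeat value used. No step asks whether the original PWV was usable. Protocol 9.6.1.4 names only PWV. That AIx is repeated as well is an inference from the SAP 5.2 baseline table, which provides for a Repeat Day 1 value of AIx, and from SAP 8.2.2, which lists AIx among the measures covered by the replacement rule. A Day 1 repeat raises no such problem: dosing waits for it and the visit clock restarts from it.

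**3. Nominal timing at Day 42.**

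| | Original reading | Repeat reading |
|---|---|---|
| Darbepoetin: days since last dose | 42 − 28 = 14 | at most 49 − 42 = 7 |
| Daprodustat: days since last dose | 42 − 41 = 1 | daily dosing continues |

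Total exposure lengthens by up to 7 days in both arms. The nominal time since last dose changes only in the darbepoetin arm. These are scheduled values; visit windows and held or delayed doses move them.

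**4. Size.** No sample size, power or variance is given for AIx or PWV. The nearest planned figure is the power of the FBF comparison, which does not bear on this point but does reproduce: ln(1.25) = 0.2231, SD = √ln(1 + 0.277²) = 0.272, 25 per arm, two-sided 5%, noncentral t gives 81.1% (stated as 80% in protocol 10.1 and 81% in the 10.1.1 table).

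Let f be the share of participants with valid AIx/PWV on both days but no QC-passing FBF pair. With the planned 50 in the PDPP, an endpoint-specific set would hold N = 50/(1 − f), rounded up. Assuming the same SD and a similar split by arm, the standard error in the PDPP is √(N/50) times that in the larger set.

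| f (assumed) | N | Extra participants | SE ratio |
|---|---|---|---|
| 5% | 53 | 3 | 1.030 |
| 10% | 56 | 6 | 1.058 |
| 15% | 59 | 9 | 1.086 |
| 20% | 63 | 13 | 1.122 |

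**The case against.** The strongest reply is that a single pharmacodynamic set, with FBF and PWV taken on the same day, is a coherent choice that makes the endpoints comparable across the same people. Enrolment was to continue until the PDPP held at least 50, so AIx and PWV would never have fallen below the planned number; the loss is only against a larger set that could have been used. And SAP 2.1 now records that the study was terminated with four completers and that only summary statistics will be reported, so there is no planned interval or test for a standard error to affect. All of this stands. It limits the size of the point, but it does not give a reason to exclude or overwrite a valid reading.

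Some stronger readings are tempting and are not supported:
- A reader might infer that repeating FBF alone overwrites PWV. It does not: SAP 8.2.2 replaces a measure only when its own procedure was repeated. Replacement happens because the protocol requires PWV to be repeated alongside FBF.
- A reader might count everyone without a QC-passing FBF pair as lost. Many of them, such as Day 1 failures and dropouts, would have no Day 42 AIx/PWV, and a Day 42 failure may be rescued by the repeat.
- A reader might treat every non-repeat darbepoetin reading as falling about two weeks after an injection. Protocol 7.1.1.2 allows doses to be held or delayed, and 9.6.1.4 has a Day 42 injection when the procedure is merely delayed.

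**Conclusion.** The point holds as a modest, cheap improvement. AIx and PWV are conditioned on FBF quality with no endpoint-specific reason given, and a valid Day 42 reading can be displaced by a later one taken, in the darbepoetin arm, after an added injection. The cost in precision depends on a share that the documents do not report; 3% to 12% on the standard error corresponds to an assumed 5% to 20%. The documents give no evidence that FBF failure differs by treatment, so no directional bias is claimed.

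After termination the practical impact is small. If all four completers passed FBF QC without a repeat, nothing displayed changes. If one did not, that is one quarter of the completers. SAP 10.1.1 reports no important protocol deviations, which is not the same as saying that all FBF data passed QC.

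**What to change.** 1. Define an AIx/PWV analysis set: randomised participants with Day 1 and Day 42 AIx/PWV readings that pass the SAP's own PWV/AIx check, keeping the condition of no important deviations and dropping the FBF QC condition. Assign Tables 3.8 to 3.10 and Listings 19 and 20 to it. SAP 8.2.2 and 10.8.4 describe a check and ranges but no exclusion rule, so the SAP should state which findings make a reading unusable.
2. Amend SAP 8.2.2 so that a repeat AIx/PWV value replaces the original Day 42 value only if the original is missing or fails that check. List both readings.
3. Reconcile the provisions for delayed visits. Protocol 9.6.1.4 has a darbepoetin dose on Day 42 when the procedure is delayed, while footnote 18 of the schedule of activities confines a Day 42 dose to a needed Repeat Day 42. The changes above do not address delayed visits.

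The cost is one population flag and a few sentences in the SAP. The downside is that the AIx/PWV and FBF sets may differ slightly and, for repeat-visit participants, the two kinds of measurement may come from different days.

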10.2.1. Treatment Comparisons

10.2.1.1. Primary Comparisons

The primary analysis of interest is the comparison of acetylcholine-induced response between daprodustat and darbepoetin alfa based on the change in FBF ratio from Day 1 to Day 42.

The pharmacodynamic per-protocol population will be used for analyzing the primary comparison.

10.2.1.2. Secondary Comparisons

The primary comparison will be repeated for the two remaining challenge agents. If an insufficient number of subjects in the PDPP population have complete Day 1 and Day 42 data for either of the two remaining challenge agents, then that challenge agent will not be statistically analysed. Instead, a summary table and subject level listing will be generated. Details regarding the exclusion from analysis will be included in the RAP. (Section 4).

Comparisons within and between treatment for daprodustat and darbepoetin alfa will be made for other PD endpoints as well.

The pharmacodynamic per-protocol population will be used for analysing all secondary comparisons.

10.3. Statistical Analyses

This section provides an overview of the analysis of data. The Reporting and Analysis Plan (RAP) which will be finalised before the interim analyses described in Section 10.3.4 are performed, will contain the full details of the planned analysis.

10.3.1. Efficacy Analyses

Not applicable.

10.3.2. Safety Analyses

All safety data will be summarised using the Safety Population.

Safety endpoints will include all AEs, clinical laboratory test parameters, HemoCue Hgb measures, vital signs, ECG parameters and physical examination.

No formal statistical analyses will be performed for the safety endpoints. These data will be listed by treatment using suitable displays for each endpoint.

10.3.3. Other Analyses (Pharmacodynamic)

The primary analysis model will be based on the acetylcholine challenge agent data.

Following log-transformation the change in FBF ratio from Day 1 to Day 42 will be analyzed using analysis of covariance (ANCOVA) model including terms for the treatment group (daprodustat/darbepoetin alfa), challenge agent dose, treatment*challenge agent dose interaction term, FBF ratio on Day 1, gender, and site stratification variable. The primary comparison of interest is the difference between treatment groups in the primary endpoint associated with the acetylcholine challenge. The point estimate and corresponding 95% confidence interval will be derived, using the residual error from the model, for the comparison of the treatment groups. These estimates will be back-transformed to provide the point estimate and corresponding 95% confidence interval (CI) for the ratio of daprodustat/darbepoetin alfa for the primary analysis.

In addition, this model will provide the supporting analysis to the primary analysis deriving the estimates and 95% CIs for (1) Change in FBF ratio from Day 1 to Day 42 for each treatment group and (2) Difference in FBF ratio between the challenge agent and saline on both Day 1 and Day 42. These estimates will be back-transformed to provide the point estimates and corresponding 95% CIs for the ratios for “Day 42/Day 1” and “challenge agent/saline” (for each challenge agent dose level) where saline is considered as providing assay sensitivity for the challenge agent.

The first secondary endpoint will use the same model as the primary endpoint with absolute FBF instead of FBF ratio as the dependent variable. The other challenge agents, sodium nitroprusside and L-NMMA, will utilize a similar model. If an insufficient number of subjects in the PDPP population have complete Day 1 and Day 42 data for either of the two remaining challenge agents, then that particular challenge agent will not

be statistically analysed. Instead, a summary table and subject level listing will be generated.

The secondary endpoints evaluating the within treatment comparison of daprodustat and darbepoetin alfa will utilize an ANCOVA model including terms for challenge agent dose, FBF measurement on Day 1, gender, and site. This model will be run for both treatment groups for each of the three challenge agents and for FBF ratio and absolute FBF.

The other secondary endpoint evaluating vascular compliance will make use of two models. The first model for augmentation index will utilize an ANCOVA model with terms for treatment group (daprodustat/darbepoetin alfa), challenge agent dose, treatment*challenge agent dose interaction term, augmentation index on Day 1, gender, and site. The second model for pulse wave velocity will utilize an ANCOVA model with terms for the treatment group (daprodustat/darbepoetin alfa), challenge agent dose, treatment*challenge agent dose interaction term, PWV on Day 1, gender, and site.

The exploratory endpoint looking at the relationship between diabetes status and endothelial function will use a similar ANCOVA model as our primary endpoint, adding in the indicator variable diabetes. This will be explored for all three challenge agents and modeled for FBF ratio and absolute FBF.

The last exploratory endpoint will analyze the FBF dose response relationships for each of the three challenge agents.

Sensitivity analyses will be performed for all endpoints analysing FBF ratio. Instead of FBF ratio, percent change from saline infusion and absolute change from saline infusion will be modelled.

Distributional assumptions underlying the statistical analyses will be assessed by visual inspection of the residual plots. Normality will be examined by normal probability plots, while homogeneity of variance will be assessed by plotting the residuals against the predicted values for the model.

Descriptive statistics (n, arithmetic mean and corresponding 95% confidence interval, standard deviation (SD), minimum, median, maximum) will be calculated by treatment group for all PD endpoints. In addition, summary of data for all FBF ratio endpoints will be provided including geometric means (and corresponding 95% confidence interval) and between-subject coefficients of variation (CVb) will be calculated by treatment group, where:

$CVb(\%) = \sqrt{\exp(SD^2) - 1} \times 100$ where SD is the standard deviation of the log_e-transformed data.

Mean (standard error [SE]) plots of the change from baseline FBF ratio data will be produced by treatment group. Separate plots will be produced for the FBF ratio for each challenge agent.

Further details will be included in the RAP.

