7.1.2.1. Acetylcholine Dosing Information

Endothelial function will be assessed by determining the vasodilator response to acetylcholine. Acetylcholine will be infused at 7.5, 15 & 30 µg/min each for 6 min per infusion into the brachial artery of the test arm.

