10. STATISTICAL CONSIDERATIONS

Statistical analyses will be performed by, or under the direct auspices of Clinical Statistics and Programming, GSK.

The null hypothesis is that there is no difference between daprodustat and darbepoetin alfa on the acetylcholine-induced change in FBF ratio at Day 42 vs the alternative hypothesis that there is a difference.

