10.1. Sample Size Determination

A sufficient number of participants will be enrolled such that at least 50 participants comprise the Pharmacodynamic Per-Protocol (PDPP) Population (See Section 10.3.1). The sample size may be adjusted following the sample size re-estimation (See Section 10.1.2).

Based on a coefficient of variation of 0.277 of change from baseline FBF ratio, a sample size of 25 participants per treatment arm, provides 80% power to show a statistically significant difference between groups, assuming a true difference of at least 25% (Cheriyana, 2011) at the alpha = 5% level of significance.

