10.3.4. Interim Analyses

An interim analysis may be conducted after approximately 24 subjects have completed the Day 42 FBF procedure, unless the blinded sample size re-estimation suggests a different sample size. If the interim analysis for this study is expected to occur after the interim analysis of the larger Phase III ASCEND program, then this interim analysis may occur sooner.

If the observed percent change between daprodustat and darbepoetin alfa for FBF ratio from Day 1 to Day 42 in response to acetylcholine is less than 8%, then the study will be stopped. Assuming a true percent change of 25% and a standard deviation of 0.272, the decision guideline was determined to have favorable operating characteristics, such as an unconditional power of <30%, and an acceptable low probability of false stop (<10%). Since the study will not be stopped for positive results, type I error will not be inflated. If the sample size changes based on the blinded sample size re-estimation, then the operating characteristics may be revised to reflect a different standard deviation. Any such changes will be documented in the RAP.

While the above is a guideline for stopping the trial due to futility, the totality of the data will be considered when making the decision at the time of the interim analysis.

Further details of the interim analysis will be included in the RAP.

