10.6.4. Pharmacodynamic

Primary/Principle Secondary/Secondary/Exploratory Endpoints
FBF Ratio/Absolute FBF

 • If either a Day 1 Repeat or Day 42 Repeat measurement is available for forearm blood flow, the repeat value will be used instead. • Forearm blood flow for a given challenge agent dose (infused arm), or for values from the non-infused arm, will be the mean of 5 continuous time point values. • Forearm blood flow ratio is defined as the ratio of a subject's treatment (infused) arm value divided by the non-treatment (non-infused) arm value 
 ○ First, the mean of both the infused and non-infused arm will be taken separately for the given five measurements before going into the ratio calculation. An example of this is shown in the table below:

CONFIDENTIAL

205767

Primary/Principle Secondary/Secondary/Exploratory Endpoints			
	Infused	Non-Infused	
Measurement 1	1.2	1.01	
Measurement 2	1.1	1	
Measurement 3	1.4	1.2	
Measurement 4	1.5	1.1	
Measurement 5	1.6	1.3	FBF Ratio
Average	1.36	1.122	1.212121212

- Absolute forearm blood flow is defined as the infused arm value.

Secondary Endpoint
PWV Dataset
For the PWV dataset, there are two recorded values for each variable per day, with the option to collect a third value if the first two values varied (Refer: SRM) too much from each other. The average of the two closest absolute values will be used for analysis purposes.

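### The primary ANCOVA in Protocol 10.3.3 implies three correlated acetylcholine records per participant but takes the treatment interval from the residual error with no participant term; for a dose-averaged contrast that interval is too narrow

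*Protocol*

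**What the plan says.** Protocol 10.3.3 gives the primary model. It is an ANCOVA on the log-transformed Day 1 to Day 42 change in FBF ratio, with terms for treatment, challenge agent dose, their interaction, Day 1 FBF ratio, gender and site. The point estimate and 95% interval "will be derived, using the residual error from the model, for the comparison of the treatment groups", and are back-transformed to one daprodustat/darbepoetin ratio. No participant effect, repeated-measures covariance or robust standard error is named.

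Protocol 7.1.2.1 sets three doses for each procedure: "Acetylcholine will be infused at 7.5, 15 & 30" µg/min. SAP 10.6.4 derives one flow value per dose and arm: "Forearm blood flow for a given challenge agent dose (infused arm), or for values from the non-infused arm, will be the mean of 5" consecutive readings.

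The design counts participants. In Protocol 10.1, "a sample size of 25 participants per treatment arm, provides 80% power", "at the alpha = 5% level of significance". Section 10 makes the test two-sided: "vs the alternative hypothesis that there is a difference".

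Protocol 10.3 and 10.3.3 leave further detail to the reporting and analysis plan. That plan (SAP 2.1, Table 1) replaces the inferential analyses with summary statistics, because the study was terminated with four completed subjects.

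**The concern.** A participant's three dose responses share the same person, session and procedure, so they can be expected to correlate positively. Randomization is by participant. Uncertainty about the treatment effect must therefore come from variation between participants, of whom 50 are planned. A residual taken over 150 rows (50 × 3) treats each row as an independent unit.

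For a contrast averaged over doses, the primary 95% interval would then cover less than 95% and the 5% test would reject too often when there is no effect. The planned diagnostics look at normality and constant variance, not independence, so they would not reveal this. The same or a similar model is planned for absolute FBF, sodium nitroprusside (SNP), L-NMMA and the diabetes analysis. The within-arm models also carry a dose term and no participant term.

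**Working it through.** **1. Records per participant.** All participants receive the same three doses. Dose and treatment-by-dose terms can be estimated only if the data hold a record for each dose. Protocol 10.3.3 also takes estimates at each dose level from this model.

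**2. The plan's own power figure.** Inputs from Protocol 10.1: "Based on a coefficient of variation of 0.277 of change from baseline FBF ratio", a 25% difference and 25 per arm.
- Log-scale SD = sqrt(ln(1 + 0.277²)) = 0.272. Protocol 10.3.4 gives the same value: "Assuming a true percent change of 25% and a standard deviation of 0.272".
- Effect = ln(1.25) = 0.2231.
- SE = 0.2719 × sqrt(2/25) = 0.0769; noncentrality = 0.2231 / 0.0769 = 2.90 on 48 degrees of freedom.
- Power by the two-sample t-test = 81.1%, against 80% in the text and 81% in the table of Section 10.1.1. All nine cells of that table reproduce within one point.

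These figures use one value per participant, so the design unit is the participant.

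**3. Effect of ignoring the correlation.** Let σ² be the residual variance of one record and ρ the correlation between two records of one participant after covariates, taken as equal for all pairs. For the difference averaged over three doses with 25 per arm:
- correct variance = (2/25) × σ²(1 + 2ρ)/3
- variance from the row-level residual = 2σ²/75
- ratio = 1 + 2ρ, so the SE is too small by sqrt(1 + 2ρ)
- actual size = 2 × [1 − Φ(1.96 / sqrt(1 + 2ρ))]

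σ cancels. Example with σ = 0.272 and ρ = 0.5: the stated SE is 0.272 × sqrt(2/75) = 0.044 and the correct SE is 0.272 × sqrt(4/75) = 0.063.

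**4. Results.** The simulation fits the stated terms with 25 per arm, three doses, three sites (SAP 5.3), a Day 1 covariate for each dose and no true effect, with 6,000 runs per ρ.

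| ρ (assumed) | Stated SE / correct SE | Size, formula | Coverage, formula | Simulated size, dose-averaged | Simulated size, single dose | Simulated size, one mean per participant |
|---|---|---|---|---|---|---|
| 0 | 1.000 | 5.0% | 95.0% | 5.6% | 5.6% | 5.8% |
| 0.1 | 0.913 | 7.4% | 92.6% | not run | not run | not run |
| 0.2 | 0.845 | 9.8% | 90.2% | not run | not run | not run |
| 0.3 | 0.791 | 12.1% | 87.9% | 12.5% | 5.3% | 4.9% |
| 0.5 | 0.707 | 16.6% | 83.4% | 17.6% | 5.7% | 4.7% |
| 0.7 | 0.645 | 20.6% | 79.4% | 21.4% | 6.3% | 5.5% |
| 0.9 | 0.598 | 24.1% | 75.9% | 25.4% | 6.5% | 5.2% |

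The formula's ceiling, at ρ = 1, is 25.8%. With two doses (SNP, L-NMMA) the variance ratio is 1 + ρ, which gives 8.6% at ρ = 0.3 and 15.5% at ρ = 0.9.

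**The case against.** **The analysis has been withdrawn.** This stands. SAP Table 1 leaves only summary statistics, so no test or interval from this model will be reported. A reader might infer that the trial's results carry inflated false-positive risk; the documents do not support that. Termination is, however, the only reason the SAP gives. It does not correct the model.

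**The size depends on an unknown ρ.** This stands. A reader might infer that the test in fact runs at 12–25%. That range needs ρ of about 0.3 to 0.95, and neither document gives any correlation. At 0.1 to 0.2 the size is 7–10%, and at zero there is no inflation.

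**The contrast is not defined.** This also stands. Section 10.3.3 does not say whether the primary comparison averages over doses or is taken at one dose, and a single-dose contrast would be nearly harmless. One overall ratio with no dose selected points to averaging, but that is a reading of the text.

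**The record structure is inferred, and detail was deferred.** This stands in part. The text never says that each dose is a separate row. It also asks the same model for agent-versus-saline estimates on each day, which the listed terms cannot supply for a change score without saline records, so the specification is incomplete. But the dose terms need a record per dose. Naming the residual as the error term is a stated rule, not an omission left for the later plan.

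**Conclusion.** The primary analysis is wrong as written in Protocol 10.3.3. A treatment effect that varies only between participants is given an error term from a residual that ignores correlation within participants.

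The size is conditional. It requires a dose-averaged contrast and positive ρ, and the figures assume equal correlation between doses. Under those conditions the nominal 5% test runs from about 7% at ρ = 0.1 to 24–25% at ρ = 0.9, and a nominal 95% interval covers about 93% to 76%.

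A reader might also infer that the sample size is wrong. It is not affected, because it was computed with one value per participant. Since the SAP has dropped inference, this is a fault in the protocol's stated plan and does not touch the descriptive results. It ranks below an error that must be corrected before reporting.

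**What to change.** In Protocol 10.3.3, choose one of two routes:
- keep the fixed terms and fit a repeated-measures mixed model with participant as subject and a within-participant covariance across doses; or
- run the ANCOVA on one dose-averaged value per participant, with treatment, Day 1 value, gender and site. In the simulation this held the size at 4.7–5.8%.

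Under either route, state that the primary contrast is the dose-averaged treatment difference, and remove the instruction to use the plain residual error. Apply the same change to absolute FBF, SNP, L-NMMA, the within-arm models and the diabetes model.

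The cost is protocol wording and a few lines of code, with no new data and no larger sample. Intervals become wider, which is correct. The protocol does not say whether 0.272 refers to one dose or to an average. If it is a per-dose SD, averaging three doses multiplies it by sqrt((1 + 2ρ)/3), which is at most 1. Normal-approximation power with 25 per arm is then 97.8% at ρ = 0.3 and 82.7% at ρ = 1, so the planned power is kept. The SAP's descriptive tables need no change on this account; the correction matters if the inferential analysis is reinstated or the model is reused.
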